responders involved in the opioid and heroin epidemic (law enforcement, firefighters, and emergency medical system personnel) compared to baseline measures and reduced stress as measured by salivary cortisol.

Specific aim #2: Determine delivery and acceptability among first responders in Appalachia. MBRT is relatively novel in this population and to our knowledge has never been applied to a broader first responder community outside law enforcement and not to our knowledge in Appalachia.

Specific aim #3: Evaluate the delivery of MBRT in an intensive 2.5 day setting with follow up remotely with an online communication method such as Skype, FaceTime, or Zoom.

Hypotheses: We hypothesize the following based on previous research:

- 1. MBRT will improve self-reported measures over the 2.5-day intensive intervention with a remote, virtual booster intervention 4 weeks after the 2.5-day initial intervention relative to baseline: a) Mindfulness and resilience, b) Physical and mental health, c) Stress and burnout, d) Emotional functioning, and e) Family functioning, f) Sense-making and decision-making.
- Pre- to post-MBRT changes in mindfulness, physical health, mental health, and stress would predict post-MBRT salivary cortisol, while controlling for pre-MBRT salivary cortisol

Design

1. Fully describe all procedures to be performed in sequential order in outline format.

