The impetus of the proposed research project came from meetings of the Great Rivers Harm Reduction Coalition, which includes public health and first responders from Cabell, Kanawha, and Putnam Counties. It was clear from discussions about the breadth and depth of the opioid and heroin epidemic that first responders are an overlooked vulnerable population in this public health crisis. Law enforcement, fire, and EMS personnel stated they need a means to cope with the daily onslaught of overdoses and interdiction efforts in addition to their daily calls and would be amenable to a resilience-building and stress-reducing intervention involving research into the effectiveness of the intervention. Subjects for the proposed research would be first responders from the three-county area, but primarily from the cities of Charleston and Huntington. Subjects will be recruited from volunteers targeting leadership and thought leaders at the frontline. Each 2.5-day intensive immersion into MBRT would be coordinated with each agency to ensure maximum participation without disrupting work schedules. Up to 35 participants will participate in each cohort. This study aims to recruit 2 cohorts from the pool of first responders in the Cabell, Kanawha, and Putnam Counties area for a minimum of 50 participants. Self-report measures will be conducted at time 0 (before the intervention), time 1 (after the 2.5-day intensive training), time 2 (4 weeks after the 2.5-day intensive training and after the week 4 remote/virtual booster training) and at time 3 (90 days after the initial intensive training). The self-report questionnaires will include the Five Facet Mindfulness Questionnaire (FFMQ), a 39item questionnaire assessing individuals' daily tendency to be mindful.² The Mindfulness Process Questionnaire (MPQ) is a 7 question self-report measure that assesses the degree how mindfulness is intentionally practiced or attempted and the ability to bring compassionate awareness to the present moment after observing the attention has drifted off or become

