
multilevel modeling approach, we plan to examine which variables significantly change from time 0 to time 1, from time 1 to time 2, from time 2 to time 3, and from time 0 to time 2 and time 3. To analyze the CAR, plan to use multilevel modeling with REML examining the main effects of phase of measurement (pre, post as above) and time after waking (0, 30, 45 minutes), as well as the interaction between the main effects. We also plan to investigate the association between the cortisol response patterns and change in mindfulness (FFMQ), stress (PSS-4), physical health, and mental health. For that purpose, we plan to analyze the area under the curve with respect to increase (AUCI) to analyze the linear relationship between each independent variable and cortisol awakening levels. Cortisol levels will be transformed into a single value by calculating the AUCI for each assessment day (1 pre and 1 post). These variables will be used in a hierarchical linear regression with pre-AUCI entered in step 1, and change in stress, physical health, mental health, and mindfulness entered in step 2, to predict post-AUCI. Alpha will be set at .05 for all analyses. The PI will be responsible for recruitment of subjects and coordinating with researchers and staff at WVU for analysis and will help oversee the implementation of the intervention. The co-PI will also assist with overseeing the intervention as well as scheduling follow-up, particularly in the Huntington community and will assist in analysis and in evaluation of difficulties. Such difficulties may include scheduling difficulties for follow-up after the intensive intervention, subject drop-out, and sustaining local resources to assist the subjects.

2. Discuss probability of group assignment to experimental and control groups.

Participants will serve as their own controls so they will participate in both the control group and the interventional group.

3. Inclusionary Criteria

Participants must meet the following inclusionary criteria to be eligible for the study: Be employed as a law enforcement official, firefighter, or emergency medical services technician or supervisor from Cabell, Kanawha, or Putnam Counties.

4. Exclusionary Criteria

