Exclusionary criteria include 1) at high risk for suicide, 2) a current psychotic disorder or significant co-morbid diagnosis (e.g., Schizophrenia, Schizoaffective Disorder, etc.), 3) high score on of 3 screening tools (PSS-4, PSQ, and DERS) with follow-on questioning which would indicate referral to a mental health practitioner, 4) primary substance use disorder.

If a patient becomes suicidal during the course of their participation in the study they will be evaluated and provided immediate intervention to ensure their safety and stabilization.

- 5. Does the research involve more than minimal risk to participants?
- 6. Describe the provisions to monitor the data to ensure the safety of participants

(data and safety monitoring plan).

a. Who will monitor the data?

All survey data will be monitored by the Principal Investigators.

b. What "data" will be monitored?

The study is composed of three general sets measures that will be monitored: primary outcome measures, secondary outcome measures, and mediating measures.

Primary Outcome Measures

The following self-assessment tools will be used:

The Brief Resilience Scale is a 6-item scale designed to assess the ability to recover from stress using a 5-point Likert scale.⁴

To measure health outcomes, the Patient Reported Outcomes Measurement Information System (PROMIS®) designed to improve self-reported in this study, we plan to use short form versions of several PROMIS domains to assess health outcomes. The Global Health Short-Form is a 10-item instrument representing multiple domains that can be scored into a Global Physical Health (GPH) component and Global Mental Health (GMH) component. Additionally, we will assess Anger (8 items), Fatigue (4 items), Sleep Disturbance (4 items), and Pain Interference (4 items). All items are rated on a 5-point Likert-type scale using various endpoints.⁵

Stress and burnout will be measured with the 4-item Perceived Stress Scale-4 (PSS-4) to assess perceived stress in life situations.⁶

The Police Stress Questionnaire (PSQ) is a 40-item questionnaire consisting of two subscales measuring operational stressors (20 job content items) and organizational stressors (20 job context items) on a seven-point Likert-type scale, ranging from 1 (no stress at all) to 7 (a lot of stress), and higher scores indicate greater stress. Nearly all the questions could be applicable to all first responder groups.⁷

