The Oldenburg Burnout Inventory (OLBI) is a 16-item measure of burnout with two dimensions: exhaustion and disengagement.8

The Emotional Intelligence Scale (EIS; Schutte et al. 1998) is a 33-item scale of emotional intelligence. Items are rated on a 5-point Likert scale ranging from 1 (strongly disagree) to 5 (strongly agree), and three items are reverse scored. All items are summed to create a total score, and higher scores indicate greater emotional intelligence.⁹

The Difficulties in Emotion Regulation Scale (DERS) is a 36-item measure that assesses clinically relevant difficulties in emotion regulation. Items are scored on six scales: lack of emotional awareness (6 items), lack of emotional clarity (5 items), difficulties controlling impulsive behaviors when distressed (6 items), difficulties engaging in goal-directed behavior when distressed (5 items), non-acceptance of negative emotional responses (6 items), and limited access to effective emotion regulation strategies (8 items).10

Family functioning will be measured through the Family Assessment Device (FAD), a 60-item measure.11 The FAD consists of six subscales and a seventh subscale (general family functioning: GFF) incorporates items from the six subscales. In this study we plan to use the 12-item GFF scale, which can be used as an indicator reflecting global family functioning. 12

Secondary Outcome Measures

Salivary cortisol is a biologic marker for stress and is a measure of the hypothalamic-pituitary-adrenal axis (HPA axis). One of the characteristics of the HPA axis is the strong circadian rhythm and the cortisol awakening response (CAR). Salivary cortisol levels are highest in the morning after awakening, and decline throughout the day and lowest around midnight, to rise again in the early morning hours. A distinct characteristic of the HPA axis is the cortisol awakening response (CAR). The CAR is characterized by a sharp rise (between 50 and 75%) of cortisol levels within the first 30 minutes after awakening. Repeated measurement of free cortisol levels within the 60 minutes after awakening in the morning is considered a stable and reliable biological marker of adrenocortical activity. We plan to collect approximately 2-3 ml of saliva at 0, 30, and 45 minutes after awakening in the morning.

Mediating Measures

Five Facet Mindfulness Questionnaire (FFMQ), a 39-item questionnaire assessing individuals' daily tendency to be mindful.²

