modeling approach with restricted maximum likelihood estimation (REML) to examine linear change over time as a fixed effect. We used REML because our data collection resulted in varying sample sizes for our measures, allowing for more accurate estimates with small sample sizes and missing data that are missing at random or completely at random ^{16,17} To test whether changes in mindfulness, emotional intelligence, and difficulties with emotion regulation (i.e., process variables) preceded changes in mental health, physical health, stress, pain interference, anger, fatigue, sleep disturbance, burnout, resilience, and family functioning (i.e., outcome variables), using the multilevel modeling approach, we plan to examine which variables significantly change from time 0 to time 1, from time 1 to time 2, from time 2 to time 3, and from time 0 to time 2 and time 3.

Aim 2 Analyses

To analyze the CAR, plan to use multilevel modeling with REML examining the main effects of phase of measurement (pre, post as above) and time after waking (0, 30, 45 minutes), as well as the interaction between the main effects. We also plan to investigate the association between the cortisol response patterns and change in mindfulness (FFMQ), stress (PSS-4), physical health, and mental health. For that purpose, we plan to analyze the area under the curve with respect to increase (AUCI) to analyze the linear relationship between each independent variable and cortisol awakening levels. Cortisol levels will be transformed into a single value by calculating the AUCI for each assessment day (1 pre and 1 post). These variables will be used in a hierarchical linear regression with pre-AUCI entered in step 1, and change in stress, physical health, mental health, and mindfulness entered in step 2, to predict post-AUCI. Alpha will be set at .05 for all analyses.

Process Evaluation

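### Hypothesis 1 spans 13 unranked primary scores tested at an unadjusted .05 with no success rule, so the error rate of a claim of improvement is undefined.

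*Combined protocol and SAP*

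**What the plan says.** All references are to the combined protocol and SAP.

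- **Hypotheses, item 1.** Self-reported measures will improve "relative to baseline: a) Mindfulness and resilience, b) Physical and mental health, c) Stress and burnout". The other three domains follow in the same sentence: "d) Emotional functioning, and e) Family functioning, f) Sense-making and decision-making". The text does not say how many of the six domains must improve, or on which score.
- **Design, item 6b.** Outcomes fall into "three general sets measures that will be monitored: primary outcome measures, secondary outcome measures, and mediating measures". The primary list is a block of instruments in no order of importance. It includes the DERS ("The Difficulties in Emotion Regulation Scale (DERS) is a 36-item measure that assesses clinically relevant difficulties in emotion regulation") and the EIS. The mindfulness questionnaires are listed separately as mediating measures ("Five Facet Mindfulness Questionnaire (FFMQ), a 39-item questionnaire assessing", and the MPQ), although mindfulness is part of domain a.
- **Design, item 6d, Aim 1 Analyses.** Change in the measures is examined by a multilevel model with linear change over time as a fixed effect. A further analysis asks whether process variables, here including emotional intelligence and emotion regulation, change before outcome variables. For that purpose it will "examine which variables significantly change from time 0 to time 1, from time 1 to time 2, from time 2 to time 3". Two longer spans, baseline to each of the last two assessments, are examined as well.
- **Design, item 1, and item 6d, Aim 2 Analyses.** "Alpha will be set at .05 for all analyses". Sidedness is not stated.
- **Design, item 6e.** The item headed decision rules deals with participant discomfort and stopping, not with inference.
- **Sample size.** Design, item 1 plans "for a minimum of 50 participants". The Sample Size section anticipates 70, from two classes of 35. There is no power calculation that would point to a primary endpoint.

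**The concern.** Aim 1, repeated under Process Evaluation, is to demonstrate improved wellbeing. Potential Benefits, item 2, says that confirming the hypothesis would give the state an effective intervention. A reader will take the stated .05 as the risk that such a conclusion is wrong. It is the risk for one test only. With many primary scores and no rule for combining them, the same results could be reported as confirming hypothesis 1 or as failing to confirm it, and the rule could be settled after the results are seen.

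The family of tests is also unsettled. The EIS and DERS are primary outcomes in item 6b but process variables in the analysis text. The plan does not say whether the PSQ, OLBI and DERS enter as totals or subscales. A rule requiring all six domains cannot be applied, because no listed instrument is described as measuring domain f.

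**Working it through.** The plan gives no calculated figure to reproduce. Its only stated inferential figure is alpha = .05.

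**Step 1: count the primary scores (Design, item 6b).**

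| Instrument | Total scores | If subscales are tested |
|---|---|---|
| Brief Resilience Scale | 1 | 1 |
| PROMIS global physical and global mental health | 2 | 2 |
| PROMIS anger, fatigue, sleep disturbance, pain interference | 4 | 4 |
| PSS-4 | 1 | 1 |
| PSQ | 1 | 2 |
| OLBI | 1 | 2 |
| EIS | 1 | 1 |
| DERS | 1 | 6 |
| FAD general family functioning | 1 | 1 |
| **Sum** | **13** | **20** |

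If the EIS and DERS are process variables, 13 − 2 = 11 total scores remain.

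**Step 2: assumptions, none of them in the documents.** Tests are two-sided at .05, so one test has a .05/2 = .025 chance of a false favourable result. No score truly changes. The slope estimates share a common correlation ρ.

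**Step 3: any one favourable slope counts.** For independent scores, P = 1 − (1 − .025)^m. With m = 13, P = 1 − .975^13 = 28.0%. For correlated scores,

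P = 1 − ∫ φ(u) · Φ[(1.96 − √ρ·u)/√(1 − ρ)]^m du.

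| Scores (m) | ρ = 0.9 | 0.7 | 0.5 | 0.3 | 0 |
|---|---|---|---|---|---|
| 11 | 6.6% | 11.1% | 15.2% | 19.1% | 24.3% |
| 13 | 6.9% | 12.0% | 16.7% | 21.4% | 28.0% |
| 20 | 7.8% | 14.5% | 21.0% | 28.0% | 39.7% |

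A simulation with t tests for 13 slopes agrees. At N = 50 it gives 16.6% at ρ = 0.5 and 20.9% at ρ = 0.3; at N = 70 it gives 16.9% and 21.4%. The sample size hardly matters.

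**Step 4: stricter rules.** Domains a to e can be measured. Assume this grouping of the 13 totals plus the FFMQ and MPQ:

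- a: Brief Resilience Scale, FFMQ, MPQ
- b: global physical, global mental, fatigue, sleep, pain
- c: PSS-4, PSQ, OLBI
- d: EIS, DERS, anger
- e: general family functioning

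The chance of a favourable slope in at least the stated number of domains, with no true change, is:

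| Domains required | ρ = 0.5 | 0.7 | 0.9 |
|---|---|---|---|
| One | 18% | 13% | 7% |
| Two | 7.5% | 6.8% | 4.8% |
| Three | 3.4% | 3.9% | 3.6% |
| All five | 0.3% | 0.9% | 1.6% |

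The choice of rule alone moves the error from well under 2.5% to several times 2.5%.

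**Step 5: effect of adjustment.** Testing 13 slopes at .05/13 = .0038, the Bonferroni level and the first Holm step, holds the chance of any false favourable slope to 2.47% at ρ = 0 and 1.88% at ρ = 0.5.

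**The case against.** **No passage says that one favourable score confirms hypothesis 1.** This is true. Domains a) to f) are listed jointly, and the most literal reading is that all should improve. Under the nearest rule that can be computed, all five measurable domains, the error is below 2.5%. So a reader might infer from Step 3 that the plan inflates the error to a known level, but the documents do not support that. They leave the rate undefined, and an inflated rate is one of the possible outcomes.

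**A reader might take 7% to 17% as the range.** Those figures belong to correlations of 0.9 to 0.5. The documents give no correlation, and at lower values the figure reaches 28%, so 17% is not a ceiling. The 2.5% comparator also rests on assumed two-sided tests.

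**A reader might say that no contrast is specified, or count every interval as a further test of improvement.** Aim 1 Analyses gives the linear slope as the analysis of change and introduces the intervals to study temporal order. What is missing is a score and a success rule. The larger figures that come from adding the intervals are therefore not relied on here.

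**This is a pilot.** The title says so, Aims 2 and 3 concern acceptability and delivery, and the effective-intervention sentence is conditional and sits in a benefits section. That lowers the stakes and favours a light fix. It does not remove the Aim 1 goal of demonstrating improvement, and the plan nowhere calls the tests exploratory.

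**Conclusion.** The concern holds in this form: the plan gives hypothesis 1 no primary score, success rule, multiplicity control or exploratory label, so .05 is not the error rate of a claim that improvement was demonstrated. That rate depends on the rule adopted.

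For 13 scores, with any one favourable slope sufficient, it is about 7% to 28% over correlations of 0.9 to 0. With all five measurable domains required, it is below 2% at correlations up to 0.9. These figures assume two-sided tests, no true change and equally correlated scores; the second also rests on the assumed grouping into domains. That the error rate is undefined follows from the text alone.

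This should be fixed. The figures cover chance only. The lack of a concurrent control is a separate matter that this change does not address.

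**What to change.** Before any post-baseline data are analysed, replace "Alpha will be set at .05 for all analyses", in Design item 1 and in Aim 2 Analyses, with one of two options.

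1. **Suited to a pilot.** State that all tests are exploratory and are reported as estimates with 95% confidence intervals. Soften the word demonstrate in Aim 1 and Process Evaluation, and the effective-intervention wording in Potential Benefits, item 2.
2. **If a confirmatory claim is kept.** Test the linear slope of each listed primary score with Holm adjustment at a familywise two-sided .05, or name one primary score and apply Holm to the rest. Claim improvement only for the scores that pass. The interval tests stay exploratory. Cortisol stays the listed secondary outcome, outside the hypothesis 1 family.

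Under either option:

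- State whether the EIS and DERS are outcomes or process variables.
- State whether the PSQ, OLBI and DERS are analysed as totals or subscales.
- Name the instrument for domain f, or remove domain f from hypothesis 1.

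**Cost.** Wording only; no added participants, visits or measures. Under option 1, no result can be offered as confirmation. Under option 2, fewer results can be called significant and power per score falls. As a guide, take a paired contrast with complete data at N = 50, by the noncentral t. The within-person change detectable with 80% power rises from about 0.40 SD at .05 to 0.56 SD at the strictest Holm step for 14 scores (.05/14 = .0036). At N = 70 it rises from 0.34 to 0.46 SD. The step for 13 scores (.0038) is almost the same.

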The overall goal of this research project is to deliver mindfulness-based resilience training (MBRT) and demonstrate improved mental and physical wellbeing among first responders involved in the opioid and heroin epidemic (law enforcement, firefighters, and emergency medical system personnel) compared to baseline measures and reduced stress as measured by salivary cortisol. Process evaluation provides a description of the acceptability of MBRT in a first responder population in Appalachia as well as the delivery of MBRT in an intensive 2.5 day setting with follow up remotely with an online communication method such as Skype, FaceTime, or Zoom.

e. What decision rules (e.g., stopping rules) will be considered?

Participants will be monitored weekly by the mindfulness instructor and if they report significant discomfort with the mindfulness intervention, they can decide

stop the study based on physical or psychological discomfort.

f. Will unexpected harms be detected promptly?

The mindfulness instructor will meet with participants in the mindfulness intervention group weekly and unexpected harm will be assessed at this time.

g. Will an increased frequency or severity of unexpected harms be detected promptly?

The mindfulness instructor will meet with participants in the intervention group weekly and unexpected harm will be assessed at this time.

h. Will the protocol be stopped once benefits are proven to outweigh harms?

We do not anticipate being able to fully assess the effectiveness of the mindfulness intervention until after the 2.5-day intensive intervention concludes.

- i. Will the protocol be stopped once harms are proven to outweigh benefits? In the extremely unlikely event that harms outweigh any benefits, the trial will be stopped.
- 7. For more than minimal risk describe how data will ensure the safety of participants.

We do not anticipate more than minimal risk with this pilot project.

8. Does the research involve surveys or questionnaires?

Yes.

a. Will you be asking questions that might distress your subjects (i.e., questions about abuse, trauma, etc.)?

No.

9. Does the research involve interviews?

Yes. Interviewing (called inquiry in mindfulness instruction) is integral to almost all mindfulness-based programs, including MBRT.

a. Will you be asking questions that might distress your subjects (i.e., questions about abuse, trauma, etc.)?

No.

10. Does the research involve data analysis?

Yes.

11. Is the research a clinical trial?

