Yes.

12. Include a literature review and explain the scientific rationale for the study.

Mindfulness-based resilience training (MBRT) is based on mindfulness-based stress reduction (MBSR) first introduced at the University of Massachusetts School of Medicine in 1979 by Jon Kabat-Zinn. The original 8-week program was designed to teach participants to use their innate inner resources to enhance awareness to the present moment experience, primarily through experiential, non-cognitive learning about the mind's capacity to create stories which may or may not correlate with what is really happening in the present. This program has been described in detail and studied rigorously in many contexts of physical and mental health.¹⁸ MBRT builds on the original 8-week course structure of MBSR and is designed to train participants in a number of experiential exercises evoking qualities of mindfulness: mental focus, sustained attention and personal and situational awareness. These exercises include versions of the body scan (body awareness exercise), sitting meditation, mindful movement, walking meditation, eating meditation, mindful martial arts exercises and other elements of MBSR. These studies demonstrated effectiveness across a wide range of measures of physical and mental health.^{1,19} Our plan is to use identical measures as the original pilot study¹ but modify the delivery after empiric unpublished observations by one of the authors, [name], that a shorter but intensive intervention was more likely to be effective than an 8-week course with a 4-week post-intervention follow-up. This study therefore builds on the demonstrated success of prior MBRT interventions with three changes: Cultural venue (Appalachia as opposed to the Pacific Northwest), includes fire and EMS in addition to law enforcement, and is presented in a 2.5-day intensive intervention with a 4-week remote follow-up (booster) and a 3-month postintensive intervention evaluation.

HIPAA

1. Does the research involve Protected Health Information (PHI) in any way?

The only PHI we will be collecting is the participant's name and phone number. This information will only be on the consenting forms which will be kept in a locked cabinet. Participant names will be in the Redcap database which is password protected.

Subjects

1. Describe in detail what will be done to identify and recruit participants?

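### Design 6g and 6i promise to detect and act on harms, but the plan records no harm data, and the weekly instructor checks do not appear in the described schedule

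*Combined protocol and SAP*

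**What the plan says.** **Harm detection.** Design 6e says "Participants will be monitored weekly by the mindfulness instructor" and lets a participant stop because of discomfort. Design 6f and 6g give the same mechanism for detecting unexpected harms and for detecting a rise in their frequency or severity: "The mindfulness instructor will meet with participants in the intervention group weekly and unexpected harm will be assessed at this time". Design 6i adds: "In the extremely unlikely event that harms outweigh any benefits, the trial will be stopped".

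**Monitored data.** Under 6a the principal investigators monitor the survey data. The 6b list consists of primary outcome, secondary outcome and mediating measures, that is, questionnaires and salivary cortisol. Under 6c monitoring takes place at times 0, 1, 2 and 3. The 6d analyses are completeness checks, descriptive statistics and models of change.

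**Unanticipated problems.** Sample Size item 3 asks how these are managed. The answer describes REDCap data capture, access and security.

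**Delivery.** There is one 2.5-day intensive and a "virtual booster intervention 4 weeks after the 2.5-day initial intervention" (Hypotheses, item 1), with a last assessment at 90 days. Specific aim 3 describes "follow up remotely with an online communication method such as Skype, FaceTime, or Zoom" and gives no frequency.

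**The concern.** 6g makes a statement about frequency and severity, and 6i about the balance of harm and benefit. Both need information on harms that someone other than the instructor can see. If the instructor's weekly impressions are neither logged nor forwarded, several mild events spread over two cohorts could each be handled sensibly without anyone seeing the pattern.

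The results are affected too. Specific aim 2 is to "Determine delivery and acceptability among first responders in Appalachia", and the Potential Benefits section looks ahead to scaling the programme across the state. How many participants were distressed or hurt by the training is basic evidence for that decision, and the plan as written would not produce it.

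A second, smaller matter is that the weekly contacts on which 6e to 6g rest are found nowhere in the description of what participants will attend.

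**Working it through.** The plan gives no figure on this point to reproduce. The check sets its sections side by side and adds two small calculations.

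**1. What each promise needs, and what the plan supplies**

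| Promise | Needs | Supplied |
|---|---|---|
| 6f: prompt detection of unexpected harm | Regular contact and someone asking | Weekly instructor meeting; mode and end date not stated |
| 6g: detection of a rise in frequency or severity | A count or log over time | None described |
| 6i: stop if harm exceeds benefit | Harm data, a reviewer, a decision | Survey data at times 0 to 3; no harm data, criterion or decision-maker named |
| Sample Size item 3: unanticipated problems | A route for recording and reporting | REDCap data handling only |

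**2. Whether another provision fills the gap**

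- The suicidality provision under Exclusionary Criteria gives a response, but no recording or reporting route.
- Design 1 has the PI and co-PI overseeing the intervention, with the co-PI helping to evaluate difficulties. The examples given are scheduling, drop-out and local resources.
- Confidentiality item 1 lets investigators identify participants in order to track outcomes. It does not describe a safety review.
- The questionnaires would show worsening on the PSS-4, DERS, global mental health, anger, fatigue, sleep disturbance and pain interference scales. None is described as asking whether the training caused distress or injury.

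None of these produces a record of harms.

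**3. Contact times**

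Take the end of the intensive (time 1) as day 0.

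- Booster and time 2: 4 × 7 = day 28.
- Time 3: day 90.
- Gaps between contacts described outside 6e to 6g: 28 − 0 = 28 days, and 90 − 28 = 62 days (62 / 7 = 8.9 weeks).
- Interval promised in 6e to 6g: 7 days.

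If the 90 days run from the start of the intensive, the second gap is 62 − 2.5 = 59.5 days; the conclusion is the same.

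These gaps show what would remain if the weekly checks did not take place. They do not show that the checks will be missed. Scoring weekly checks as unmatched because only 6e to 6g mention them would be circular, so no such fraction is given.

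**4. What a record would allow**

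Suppose all n participants answer and none reports a harm. The one-sided 95% upper limit on the share harmed is 1 − 0.05^(1/n).

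- n = 50 (Design 1, "for a minimum of 50 participants"): 1 − 0.05^(1/50) = 5.8%.
- n = 70 (Sample Size item 1, planned enrolment): 1 − 0.05^(1/70) = 4.2%.

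These are general zero-event limits. They illustrate what the pilot could state with a record and do not measure the defect.

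**The case against.** The strongest reply is that 6e to 6g are themselves part of the protocol and do promise weekly contact. A safety check need not be repeated in a list of training sessions and questionnaire times. Specific aim 3 allows remote follow-up without limiting it to the booster, and Confidentiality item 5 permits any contact that the protocol calls for. This stands. A reader might infer that the weekly meetings contradict the schedule and will not happen; the documents do not support that. Potential Risks/Discomforts item 2 places instructor contact at the intensive and at worksites without mentioning weekly meetings, but it also omits the remote booster, so it is not a complete list.

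A reader might also infer that the weekly wording was carried over from the 8-week course that this delivery replaces. Design 12 does not say that the course met weekly, and nothing shows where the wording came from.

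The surveys are a fair defence in part. Counts of participants who worsened can be drawn from them, so it would be wrong to say that the pilot can report nothing on distress. What remains missing is attribution to the training, and injury. A self-attribution item in a single-arm study is imperfect causal evidence, but it is direct information that no listed measure is described as collecting.

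Finally, the study is declared minimal risk, people at high risk are excluded, and consent material is not available here, so any harm-reporting instruction in it cannot be checked. These points limit the importance. They do not supply a count for 6g.

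**Conclusion.** The concern holds in this form: the plan promises to detect a rise in harms and to stop if harm outweighs benefit, yet no harm item is collected and no step records, counts or forwards the instructor's findings. 6g therefore has no count, and 6i has only indirect survey data. The absence of the weekly contacts from the described schedule is a secondary, unreconciled mismatch.

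It would go too far to say that the trial has no safety provision. It has instructor checks, a right to stop, a suicidality response and investigator review of survey data.

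Importance is low to moderate. No efficacy estimate changes, and what is lost is the ability to see and report training-attributed harms. The conclusion assumes that the consent material adds no recording route from the instructor to the investigators. The change is worth making because it is cheap.

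**What to change.** 1. Add to 6b one private REDCap item at times 1, 2 and 3 on distress or injury that the participant attributes to the training.
2. Have the instructor keep a short log of reported discomfort, harms and stops, and send it to the principal investigators.
3. In 6i, have the principal investigators review both sources at times 1, 2 and 3, and at once after any suicidality or any training-attributed event that needs care. Each review ends in a documented decision to continue, modify or stop.
4. Report harm counts with the results.
5. Keep the weekly checks as brief remote contacts, and state their mode and end date. If they are dropped, reword 6e to 6g to the contacts that exist and acknowledge the gaps of about 28 and 62 days, which sit poorly with prompt detection in 6f.

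The cost is one extra questionnaire item, a short log, a brief review by existing staff and some instructor time for the weekly contacts. No added visits, participants or changes to the efficacy analysis are needed.
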